AIM 3: To explore the relationship between obesity, attitudes (barriers, motivation) towards physical activity, and physical activity levels in a well-characterized longitudinal cohort of older women with UI symptoms. **Hypothesis 3.** Older women with UI view UI severity as a barrier to a high physical activity. Lower physical activity levels (defined as <6.2 MET hours/week) in women with UI impacts on physical performance and is associated with obesity. Physical activity levels will be determined using the Community Healthy Activities Model Program for Seniors questionnaire that reports metabolic equivalent task (MET) hours/week.(6) Questionnaires will assess barriers to and motivations for physical activity.

METHODS AND MEASURES:

Study Design:

We plan a prospective cohort study with an adaptive design based on physical function status. The design will involve tracking the number of women recruited with physical function impairment and those without any functional impairment. We aim to recruit similar numbers of women in each group. If we find unequal numbers, we will adapt our recruitment strategies based on a woman's functional status.

We will compare changes in outcome measures within and between groups after 6 and 12 weeks of PFME. The change in pelvic floor strength/efficiency will be assessed by repeating the pelvic floor PERFECT assessment and will be compared between groups. Changes in UI symptoms, symptom severity, and impact of UI symptoms on quality of life will be determined using standardized measures described above. Data analysis will define associations between changes in PERFECT measures and the change in UI episodes (based on 3-day voiding diary), severity, and type (based on QUID-7), and impact on quality of life (PFIQ-7) within and between groups. Objective measurement of lower-extremity strength will inform the relationship between lower-extremity strength, pelvic floor strength, and UI symptoms at baseline and the 6-week visit. (See Appendix Figure 1 – Study Flow Chart)

Setting:

Study visits will take place at the Sticht Center on Aging in the Geriatric Research Clinic. The study coordinator will meet the participants in the GRC to confirm eligibility, describe the study, answer any questions, and administer written informed consent.

Subject selection criteria:

- **Inclusion criteria:**
 - a) Women, age 70 years or older
 - b) Symptoms of Urinary Incontinence for greater than 6 months

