(Defined by the QUID assessment as having subscale score for stress ≥ 4 , and/or urge score ≥ 6 , and/or total QUID score ≥ 10)
 - c) Willing and able to be compliant with pelvic floor muscle exercise intervention (standard of care) for 12 weeks and to log compliance
 - d) Willing and able to undergo an extensive physical function evaluation
 - e) SPPB ≤ 9 (for any new screens conducted after amendment 12 is approved)
- **Exclusion criteria:**
 - a) Prior surgical intervention for urinary incontinence within the past 12 months
 - b) Hysterectomy within 12 months
 - c) Having primarily nocturia
 - d) Diagnosis of:
 - i) Pelvic Organ Prolapse beyond the hymenal ring
 - ii) Urogenital Fistula
 - iii) Neurogenic Overactive Bladder (associated with a diagnosis of Multiple Sclerosis or Stroke within past 12 months)
 - iv) Incomplete Bladder Emptying/Urinary Retention with PVR >150 ml (measured by bladder scan)
 - e) Wheelchair bound
 - f) Having significant cognitive impairment or dementia
 - g) Unsafe to exercise (severe cardiopulmonary disease)
 - h) Unable/unwilling to provide informed consent
 - i) Determined otherwise ineligible by the principal investigator

Sample Size Estimate:

With 50 women per group (functional impaired and non-impaired) and assuming a drop-off rate of 15% for a two-sided test, we will be able to detect a 20% difference of improvement of UI episodes (assuming a standard deviation of 32%)[40] with at least a power of 80% at 0.05 significance level for Aim 1.

Interventions and Interactions:**Interaction 1: Mailing of Introductory Letters**

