Study visit 3 (week 6): (2.5 hours) This visit will take place 6 weeks after initial assessment to assess for changes in pelvic floor strength/function, physical performance, and physical activity. They will bring with them a 3-day voiding diary and 4 weeks of PFME compliance calendars. A subset of assessments from Study Visit 1 will be repeated.(see Table 1) Additionally, self-reported Global Impression of Improvement (GPI), Patient Satisfaction Questionnaire (PSQ), and Estimated Perception of Improvement (EPI) will be assessed using a standardized and validated measure for UI,[39]. To improve recruitment and retention, a \$30 gift card or check will be provided at the completion of this visit.

Study Visit 4 (week 12): (2 hours) To observe long-term adherence to PFME therapy and evaluate the sustained effect on UI symptoms, participants will be asked to return for a visit. They will bring with them a 3-day voiding diary and 6 weeks of PFME compliance calendars. A subset of assessments from Study Visit 1 will be repeated (see Table 1). Additionally, self-reported Global Impression of Improvement (GPI), Patient Satisfaction Questionnaire (PSQ), and Estimated Perception of Improvement (EPI) will be assessed using a standardized and validated measure for UI. [39] We will invite 30 participants (15 with poor physical function defined by SPPB < 9 and 15 with normal physical function defined by SPPB >10) to complete repeated physical performance measures (SPPB, grip strength, postural sway) in order to establish variance among this cohort at 12 weeks. To improve recruitment and retention, a \$30 gift card or check will be provided at the completion of this visit.

Reminder telephone calls: Our study staff will call participants 3 days prior to study visit 2, study visit 3 and 4 to remind them to complete the diary and of the time/date of the appointment. In addition, compliance calls will be made in between study visits 3 and 4 every 2 weeks to check on adherence to the PFME prescription, remind participants of upcoming visits, and review expected completed documentation.

Data Entry:

Outcome measures:

Pelvic floor assessment	

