Pelvic examination	External evaluation of pelvic floor support will be performed by the PI or physical therapist (per mentioned above). The patient will be asked to undress from the waist down. She will be placed in the dorsal lithotomy position. While her head is elevated to 45 degrees, she will be asked to perform the Valsalva maneuver. The labia majora will be parted to allow visualization of the urethra and vaginal introitus. During the Valsalva maneuver, the anterior and posterior vaginal wall will be observed to ensure that pelvic organ prolapse is not present at or below the level of the vaginal

	hymen. The vaginal epithelium will be assessed visually for signs of urogenital atrophy.
Pelvic Floor Muscle Exercise (PFME) prescription using the PERFECT scheme	The PERFECT scheme is a valid and reliable pelvic floor assessment tool to assess pelvic floor muscle strength and efficiency.[22] PERFECT stands for: P= power (a measure of strength using digital exam or manometric perineometer), E=endurance (how long can they hold the contraction), R=repetitions (how many repetitions can they sustain), F=fast contractions (how many contractions can be repeated), ECT = every contraction timed (how long do they hold the fast contractions). Power is measured by assessing 3 contractions of maximal effort and obtaining a mean strength measurement. Objective measurement of perineal power will be performed using a perineometer. A prescription will be provided for each participant based on their individual PERFECT assessment and typically entails a number of repetitions, duration of squeeze, and number of sets. .
Physical function and performance measures	
Extended version of the Short Physical Performance Battery (expSPPB)	The expSPPB is a standard and robust predictor for disability that includes progressively more challenging standing balance tasks held for 10-30 seconds each (side-by-side, tandem, and semi-tandem, single leg), 4-meter walk to assess usual gait speed, 4-meter narrow walk test of balance, and five chair-stands test.[26] It more sensitively detects changes in physical performance by decreasing the ceiling effect present in healthier adults.[27] The timed 4-meter walk will be performed as a surrogate for the 6-meter walk; it is associated with urgency/stress UI and its results are strong predictors of falls and fractures in women.[28]

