The hypothesis for AIM 1 (Primary) will be tested using analysis of covariance (ANCOVA) to compare differences of efficacy of PFME therapy (i.e. % UI episodes/week reduction at week 6) between women with and without functional impairment, adjusted for age, race/ethnicity, and BMI. Differences in least-squares means and associated 95% confidence intervals will be calculated. For Sub-aim 1(a), attitudes (barrier and motivation) towards physical activity will be compared between higher vs. lower physically active women using Chi-Square tests. For Sub-aim 1(b), association between physical activity (lower vs. higher) and UI severity will be tested using logistic regression, adjusting for age, race/ethnicity and BMI. Odds ratio and associated 95% confidence intervals will be calculated. We will also explore the impact of functional impairment on the association by adding an interaction of functional impairment and UI severity. Similar ANCOVA models as for Aim 1 will be used to compare efficacy of PFME therapy between women with and without sarcopenia (AIM 2) and between women with and without mild cognitive impairment (Aim 3).

Potential Pitfalls and Alternative Solutions:

- a) **Recruitment:** Women will be recruited from the community in the catchment area for Wake Forest Baptist Health system, which includes central and western North Carolina and south central Virginia. Last year, we saw 476 women with a urinary incontinence diagnosis. More than 30% of women older than 70 have UI symptoms and an equal number will have functional impairment. Therefore, we do not expect difficulty in recruiting 50 eligible women/year over 24 months. The Wake Forest Sticht Center on Aging has an established database of older volunteers for aging-related research (VITALS database=12,600) that will also be a source of recruitment. If necessary, we may start targeted recruitment to ensure that ~ 50% of potential participants have a SPPB score > 10 and that 50% have scores of ≤ 9 .
- b) **Adherence to PFME therapy:** Participants will receive a calendar with their PFME prescription on it and places on the calendar to document compliance. They will be contacted by study staff every 2 weeks to assess for compliance and to reinforce adherence to therapy. This approach has resulted in good compliance in other trials of elderly adults run by the Sticht Center.

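### If one baseline SPPB score both forms the function groups and starts the change, regression to the mean biases the unadjusted comparison of change in physical performance

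*Combined protocol and SAP*

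**What the plan says.** All references are to the combined protocol and SAP.

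- **Comparison.** Study Design: "We plan a prospective cohort study with an adaptive design based on physical function status". Then: "We will compare changes in outcome measures within and between groups after 6 and 12 weeks of PFME".
- **Groups.** Potential Pitfalls (Recruitment) describes optional targeting so that about "50% of potential participants have a SPPB score > 10 and that 50% have scores of ≤ 9". Study Visit 4 takes a subset of 30: "15 with poor physical function defined by SPPB < 9 and 15 with normal physical function defined by SPPB >10". Inclusion criterion e) is "SPPB ≤ 9 (for any new screens conducted after amendment 12 is approved".
- **Outcome.** The Outcome measures table lists the expSPPB and says of it: "It more sensitively detects changes in physical performance by decreasing the ceiling effect present in healthier adults". One stated purpose of Study visit 3 is "to assess for changes in pelvic floor strength/function, physical performance, and physical activity". Appendix Table 1 schedules the expSPPB at baseline and week 6 for everyone, and at week 12 for the subset.
- **Model.** The Analytical Plan specifies ANCOVA for percentage reduction in UI episodes, with age, race/ethnicity and BMI as covariates. It gives no model for change in expSPPB, and no baseline value of any outcome enters as a covariate.
- **Pre-screen score.** The text under Interaction 2 allows a separate pre-screen visit for the SPPB but does not require it. It does not say which SPPB assigns the group or which serves as baseline.

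**The concern.** An SPPB score is true function plus day-to-day error. Women at or below 9 include some who had a poor day, and women above the upper cut include some who had a good one. Measured again, the low group drifts up and the high group down. If change is taken from the same score that sorted the women, this drift is counted as change.

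The study has no untreated arm, so nothing in the design would expose the artefact. A rise in impaired women, set against a fall in unimpaired women, could be read as PFME improving physical performance where function is poor. Women screened after amendment 12 enter only if they score 9 or less, so their within-group change is exposed even without a comparison group.

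**Working it through.** **The plan's own figure.** Sample Size Estimate: 50 per group, 15% drop-out, difference 20%, SD 32%, two-sided 0.05. Evaluable: 50 × 0.85 = 42.5 per group. Power = Φ(20 / (32 × √(2/42.5)) − 1.96) = Φ(2.88 − 1.96) = 0.82. The stated 80% is reproduced. It concerns UI episodes; the documents give no corresponding figure for SPPB or expSPPB.

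**Inputs for the check.** From the documents: cut-offs ≤9 and >10 (also ≥10, because a score of exactly 10 is otherwise unassigned), and 42 per group. Assumed: SPPB mean 9, 9.5 or 10; SD 2; test–retest reliability r of 0.7, 0.8 or 0.9; no true change.

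**Model.** True score ~ N(mean, 2√r). Each visit adds independent error with SD 2√(1−r), and scores are rounded and held to 0–12. The baseline score both assigns the group and starts the change.

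- Between groups: z = (d_low − d_high) / √((s_low² + s_high²)/42)
- Within the impaired group: z = d_low / (s_low/√42)
- Chance of rejection ≈ Φ(z − 1.96)

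Example with mean 9.5 and r = 0.8: d_low = +0.35 (SD 1.28) and d_high = −0.35 (SD 1.10) for ≥10. Between groups, z = 0.70/√((1.28² + 1.10²)/42) = 2.7, giving 77%. Within the impaired group, z = 0.352/(1.28/√42) = 1.78, giving 43%.

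| Mean | r | Change ≤9 | Change ≥10 | Change >10 | Within ≤9 | Between, ≥10 | Between, >10 |
|---|---|---|---|---|---|---|---|
| 9 | 0.7 | +0.41 | −0.61 | −0.82 | 42% | 91% | 98% |
| 9 | 0.8 | +0.29 | −0.42 | −0.58 | 30% | 76% | 92% |
| 9 | 0.9 | +0.16 | −0.23 | −0.32 | 18% | 50% | 70% |
| 9.5 | 0.7 | +0.51 | −0.50 | −0.70 | 59% | 91% | 98% |
| 9.5 | 0.8 | +0.35 | −0.35 | −0.49 | 43% | 77% | 92% |
| 9.5 | 0.9 | +0.19 | −0.19 | −0.27 | 26% | 50% | 70% |
| 10 | 0.7 | +0.62 | −0.41 | −0.59 | 76% | 93% | 99% |
| 10 | 0.8 | +0.43 | −0.28 | −0.41 | 59% | 80% | 93% |
| 10 | 0.9 | +0.23 | −0.16 | −0.23 | 35% | 52% | 71% |

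The nominal rate is 5% throughout. Simulated t-tests agree to within about 5 percentage points. At r = 0.95 (mean 9.5) they still give 15% within the impaired group and 31% (≥10) or 46% (>10) between groups.

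**SPPB for grouping, expSPPB for outcome.** Let ρ be the correlation of the two scores' errors at the same visit. For a cut at the mean, in SD units, D = 2 × 0.798 × ρ(1−r), v = 2(1−r) − 0.637[ρ(1−r)]², and z = D/√(2v/42). At r = 0.8, between-group rejection is 67% for ρ = 1, 42% for ρ = 0.75, 21% for ρ = 0.5 and 5% for ρ = 0.

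**Remedies under the same null.** Grouping on a separate earlier score and measuring change from a fresh baseline gives mean change near zero in both groups and rejection of about 4–8%. ANCOVA of the follow-up score on group and baseline score gives 5–7% (≤9 vs ≥10) or 7–8% (≤9 vs >10).

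**The case against.** The strongest reply is that this analysis is not written down. The Study Design sentence is general. The sentences after it name PERFECT measures, UI episodes, QUID and PFIQ-7, not the expSPPB, and the Analytical Plan models only UI-episode reduction. That is so. But the expSPPB is a listed outcome, week 6 is meant to assess change in physical performance, and the only comparison stated for outcome measures in general is an unadjusted one by group. Following the plan as written leads to the biased contrast.

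Second, the grouping rule is not fixed. The ≤9 versus >10 split belongs to a recruitment contingency, and Aim 2 defines sarcopenia with functional impairment by grip strength or gait speed. This stands as a limit on the size. The direction would be the same for any repeated measure that also forms the groups.

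Third, SPPB and expSPPB are different scores with an unknown share of common error. This also stands, and it could shrink the effect considerably.

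A reader might infer that a significant gain in impaired women is assured. It is not: that test rejects in about 18–76% of null trials, and the between-group test is the more exposed. A reader might also infer that the week-12 subset is the worst case. The mean shift is larger there (0.55–1.44 points for <9 versus >10), but Study Visit 4 says the subset is for establishing variance, not for testing change.

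**Conclusion.** The concern holds for change in SPPB or expSPPB when one baseline score both forms the groups and starts the change. The direction of the bias is then certain: up in the impaired group, down in the unimpaired group. Its size is conditional. With mean 9–10, SD 2, reliability 0.7–0.9, one score in both roles and 42 per group, the false between-group difference is about 0.4–1.2 points. Rejection is about 50–93% for an upper group of ≥10 and 70–99% for >10. The documents supply none of the SPPB figures behind these rates, and the rates fall toward 5% as the errors of the two scores become less correlated.

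The documents do not support extending this to the primary analysis: percentage reduction in UI episodes is not the grouping variable and is not affected. Nor do they show that the study intends to claim a PFME benefit for physical performance; no aim or hypothesis says so. This is a bias in a secondary comparison that the plan invites and does not guard against.

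**What to change.** In Study Design and the Analytical Plan:

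1. State which SPPB score assigns the group and which score is the baseline for change.
2. Where a pre-screen SPPB exists, use it for eligibility and grouping, and use the visit-1 score as the baseline for change.
3. Where it does not exist, do not test unadjusted between-group change in SPPB, expSPPB or 4-metre gait speed. Either drop that contrast or use ANCOVA of the follow-up score with the baseline score as a covariate.
4. Report within-group SPPB or expSPPB change, including that of women enrolled under criterion e), as subject to regression to the mean and not as a PFME effect.

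The cost is wording only. One secondary contrast is dropped or becomes less precise. For a cut at the mean of a normal score, group and baseline correlate about 0.80, so adjustment multiplies the standard error of the group term by about 1/√(1 − 0.64) = 1.67 for a given residual variance. No extra visits are needed, since the pre-screen score is used only where it already exists.

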AIM 1: To robustly characterize the relationship between physical performance, functional impairment, and sarcopenia status of community-dwelling older women with UI in up to 100 women.

Hypothesis 1. Functional impairment and sarcopenia will be prevalent among older women seeking care for UI and will negatively correlate with UI severity in a diverse sub-specialty-based clinic population.

Urinary incontinence will be defined as bothersome involuntary leakage of urine at least 2 times/week and characterized by 3 day voiding diary. Physical and functional performance will be measured using the extended Short Physical Performance Battery, a timed 400 meter walk, and Isokinetic dynamometer (Biodex). Sarcopenia status will be determined by the composite of an Appendicular skeletal muscle mass index (ASMI) <5.5 kg/m², usual walk speed <1 m/s, and hand-grip strength ≤ 20.5 kg.

AIM 2: To compare a well-characterized cohort of functionally impaired older incontinent women to a control group of functionally normal older incontinent women to assess the impact of sarcopenia and functional impairment on efficacy of a standardized 6 week PFME prescription for treatment of UI.

Hypothesis 2. Functional impairment and sarcopenia status will be independent predictors of efficacy of PFME therapy in a well-characterized cohort of older women with UI. Specifically, older incontinent women without functional impairment will have greater improvement in UI episodes after PFME therapy in comparison to those with functional impairment. Sarcopenia with functional impairment will be defined as a grip strength <16 kg or gait speed <1 m/s. We expect a 6 week PFME prescription to decrease UI episodes by 50% defined in a 3 day bladder diary and the full 12 weeks to decrease UI episodes even more. Pelvic floor strength will be objectively measured using the PERFECT assessment and perineometer.

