- c) **Dropouts:** Participants who drop out will be contacted by the PI or study coordinator to assess why. They will be offered assistance to help facilitate study completion (e.g., transportation to get to appointments). If they are not willing to return, we will ask that they complete 3-day voiding diary and PFME therapy and mail in the diaries and compliance calendars to the study staff in an attempt to ensure that we collect our primary outcome data. If they comply, they will be provided with a \$30 gift card.
- d) **Reproducibility and representativeness of participants to general population:** We plan to recruit from a diverse community of older women, including underserved, underinsured, and insured patients.

We have a mixed ethnic population of black, non-Hispanic white, and Hispanic Americans in the catchment area; the study will reflect the general population (see Human Subjects section).

Human Subjects Protection

Recruitment & Identification of Cohort:

Potential participants will be recruited from the community of patients in the Wake Forest Baptist Health System and those in a database of older adults interested in volunteering for research studies on aging (the VITAL database in our Sticht Center on Aging). We plan to employ 3 specific recruitment approaches:

- 1) The electronic health record will be searched using the Translational Data Warehouse (managed by the Wake Forest Clinical and Translational Science Institute [CTSI]). Women >70 years old with ICD-10 diagnosis codes [R32 (unspecified UI), N39.81 (functional UI), N39.41 (urge UI), N39.46 (mixed UI), and N39.3 (stress UI)] will be identified as having a diagnosis of UI within 6 months of the query. Potential participants will be mailed a letter introducing them to the study, informing them that they may be eligible to participate and will be contacted within 2 weeks by study staff in order to inquire about their interest to participate. We will include the 6-item Questionnaire for Urinary Incontinence Diagnosis (QUID) validated to establish the diagnosis, distinguish UI type, and measure severity of UI in the letter [18]. It is common for women to self-identify the presence of UI symptoms. Interested women will be instructed to call our study coordinator to learn more.

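### The week-12 diary enters no named efficacy analysis, so the promised 12-week comparison and the hypothesised further gain have no planned test, and missing week-6 diaries have no analysis rule

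*Combined protocol and SAP*

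**What the plan says.** **Promise.** The Study Design section says changes in outcome measures will be compared "within and between groups after 6 and 12 weeks of PFME". Hypothesis 2, under Aim 2, expects a halving of incontinence (UI) episodes on the 6-week exercise prescription and "the full 12 weeks to decrease UI episodes even more". The description of Study Visit 4 gives the week-12 visit two purposes: long-term adherence and the durability of the effect on symptoms.

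**Data.** The 3-day diary is collected at baseline (returned at week 2), week 6 and week 12, according to the UI assessment text and the assessment schedule in the Appendix.

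**Analysis.** The Analytical Plan compares percent "UI episodes/week reduction at week 6" between women with and without functional impairment, by ANCOVA adjusted for age, race/ethnicity and BMI. It calls this Aim 1 (primary), although the Objectives list the same question as Aim 2. Similar ANCOVAs follow for sarcopenia and for mild cognitive impairment. The remaining methods are chi-square tests on attitudes and a logistic regression on physical activity.

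**Missing data.** The Sample Size Estimate is "assuming a drop-off rate of 15% for a two-sided test". Under Potential Pitfalls, item c, women who drop out are asked to mail in diaries "in an attempt to ensure that we collect our primary outcome data". No rule is given for analysing diaries that remain missing.

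**The concern.** A model with one follow-up visit as its response can estimate neither a week-12 group difference nor a change from week 6 to week 12. Both are announced, and the second is a directional hypothesis. Without a planned analysis, the response scale, the covariates, the set of women included and the treatment of missing diaries at week 12 would all be chosen once the data are in hand. A reader of the results could not tell a planned week-12 finding from a selected one.

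The second issue is smaller. An ANCOVA on the week-6 value uses only women who have that value. A woman who misses week 6 but supplies a week-12 diary contributes nothing, even though her later diary carries information about her week-6 response. Nothing in the plan says how far the result depends on women who supply no follow-up diary at all.

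**Working it through.** **1. Promise against analysis**

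| Announced | Where | Named analysis |
|---|---|---|
| Between-group comparison, week 6 | Study Design | ANCOVA |
| Between-group comparison, week 12 | Study Design | none |
| Within-group change, weeks 6 and 12 | Study Design | none |
| Further fall from week 6 to week 12 | Hypothesis 2 | none |
| Missing diaries | Potential Pitfalls, c | retrieval only, no analysis rule |

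**2. The plan's own power figure.** Inputs from the Sample Size Estimate: difference 20 points, SD 32 points, two-sided 0.05, 50 per group, 15% loss.

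- Required n per group = 2 × (1.960 + 0.842)² × (32/20)² = 2 × 7.85 × 2.56 = 40.2, so 41.
- Allowing for loss: 41/0.85 = 48.2, so 49, against 50 planned.
- Evaluable: 50 × 0.85 = 42.5 per group. Power at 42 is 0.808 by the noncentral t (0.817 by the normal approximation). At 42.5 the normal approximation gives 0.822.

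The claim "with at least a power of 80% at 0.05 significance level for Aim 1" therefore holds, and it already treats the lost 15% as contributing nothing.

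**3. What a joint model adds to the week-6 contrast.** Assumptions not in the documents: SD 32 at both visits, between-visit correlation ρ of 0.3 to 0.8, and a share of the 7.5 women per group missing week 6 who supply a week-12 diary, from none to all. Call the number who supply one m. With 42.5 women per group having both diaries, and data missing at random, the maximum-likelihood variance of a week-6 group mean is

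32² × [(1 − ρ²)/42.5 + ρ²/(42.5 + m)],

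and the effective n is 32² divided by that variance. For ρ = 0.8 and m = 7.5: 0.36/42.5 + 0.64/50 = 0.02127, so the effective n is 47.0.

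| Share with a week-12 diary | ρ = 0.3 | ρ = 0.5 | ρ = 0.8 |
|---|---|---|---|
| None | 42.5; 82.2% | 42.5; 82.2% | 42.5; 82.2% |
| Half (m = 3.75) | 42.8; 82.4% | 43.4; 82.9% | 44.8; 84.1% |
| All (m = 7.5) | 43.1; 82.7% | 44.2; 83.6% | 47.0; 85.8% |

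Each cell gives effective n per group and normal-approximation power. The largest gain is 85.8 − 82.2 = 3.6 points; the smallest is zero.

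**4. Whether the week-6-to-12 hypothesis can usefully be tested.** The SD of the change is 32 × √(2(1 − ρ)): 37.9 at ρ = 0.3 and 20.2 at ρ = 0.8. Detectable effects at 80% power, with 42 women per group having both diaries (multiplier 2.80):

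| Contrast | ρ = 0.3 | ρ = 0.8 |
|---|---|---|
| Further gain, both groups pooled (84 women) | 11.6 points | 6.2 points |
| Further gain within one group (42) | 16.4 points | 8.8 points |
| Group difference in further gain | 23.1 points | 12.4 points |

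The pooled further gain can be estimated with useful precision from data already scheduled. The group difference in further gain is imprecise unless ρ is high, and should be read as secondary.

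**The case against.** **Week 6 is a coherent primary time point.** Aim 2 concerns a 6-week prescription, and week 12 can be seen as follow-up of adherence and durability. This stands, and is why the week-6 contrast should remain primary. It does not supply an analysis for the week-12 comparison that the Study Design section promises.

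**A separate week-12 ANCOVA and a paired comparison would close the gap.** True. The joint model is preferred because it gives the same contrasts and also uses the diaries of women seen at only one follow-up visit.

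**The plan does not say it will drop anyone.** A reader might infer a complete-case rule. The documents state none, and the mail retrieval may well recover the week-6 diary itself. Only the default behaviour of the named model, for diaries still missing, can be criticised.

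**The ANCOVA is not the only analysis.** A reader might take it to be so, but chi-square tests and a logistic regression are also planned, and the Study Design section mentions associations between change in pelvic floor measures and change in episodes. None of these is a week-12 efficacy comparison.

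**No power is lost.** A reader might infer that the single-visit model leaves the study short, or that using both visits raises power greatly. The sample size already allows for the loss. A large gain would belong to a contrast averaging the two visits, which is not the plan's primary question.

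**Unequal loss between groups is not shown.** It might be inferred because the groups differ in physical function, but the documents give no group-specific rates. Loss that differs only by group would not in itself bias a model containing group.

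**Conclusion.** The gap is real and can be read directly from the text: the only models planned for change in UI episodes are week-6 ANCOVAs, the week-12 diary enters no named efficacy analysis, and the hypothesis of further gain has no test. There is also no analysis rule for week-6 diaries that stay missing.

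The stated sample size and power are correct (0.808 at 42 per group), and no larger study is needed. For the week-6 contrast a joint model adds about 0 to 4 percentage points of power, on the assumed correlation of 0.3 to 0.8 and the full range of week-12 return. The case for change rests on pre-specifying the promised comparisons and on validity under missing at random, not on power. It is an inexpensive improvement that should be made; it does not undermine the week-6 primary analysis.

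**What to change.** Replace the single-visit ANCOVA with one repeated-measures model:

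- **Response:** percent reduction in UI episodes at weeks 6 and 12, from all available follow-up diaries.
- **Terms:** group, visit, group-by-visit, age, race/ethnicity, BMI and baseline UI episodes. Baseline enters as a covariate, not as a repeated response, because percent reduction from baseline has no meaning at baseline.
- **Covariance:** unstructured, or robust standard errors.
- **Primary contrast:** group difference at week 6, as now.
- **Named secondary contrasts:** group difference at week 12, and the week-6-to-12 change within and between groups.
- **Sensitivity analysis:** women with no follow-up diary set to no improvement (0% reduction).

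Apply the same structure to the sarcopenia and cognitive-impairment comparisons, which are already defined by reference to the primary model.

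The cost is SAP wording and slightly more analysis work, with no new data and no larger sample. The model relies on a missing-at-random assumption and a covariance assumption. Robust standard errors protect against the second; the sensitivity analysis probes the first.
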